5.2 Study Population

The target population will consist of subjects ≥ 18 years in age, who are being implanted with a Micra AV per approved indications for use.

5.3 Study Procedures

After subject enrollment, study procedures will consist of collecting subject's medical history, physical exam, cardiovascular medications, and device implant information. During the Micra AV implant, additional study-specific data will be collected including: accelerometer and EGM waveforms (either paper strips or electronic form) and device interrogations. Immediately following implant, a Holter will be placed for approximately 1 hour to record data related to the device's Atrial Sensing Setup process.

Within 48 hours of the Micra AV implant, an echocardiogram will be performed. Prior to the echocardiogram, the atrial sensing will be reviewed and optimized, if necessary.

One month after the Micra AV implant, the subject will come into an in-clinic setting for the 1-month post-implant visit. A Holter monitor will be placed on the subject to record accelerometer, EGM, and ECG waveforms and device-specific markers. The atrial sensing will be reviewed and optimized, if necessary. Overall, approximately 30 minutes of data will be collected during the in-clinic visit with approximately 20 minutes collected at rest. The subject will then be given an activity log to be filled out

and will wear the Holter monitor for approximately 24 hours. The Holter can be returned in-person or sent back in a pre-addressed package.

Three months after the Micra AV implant, the subject will come back for the final in-clinic 3-month post-implant study visit. A Holter monitor will again be placed on the subject to record accelerometer, EGM, and ECG waveforms and device-specific markers. The atrial sensing will be reviewed and optimized, if necessary. Overall, approximately 30 minutes of data will be collected during the in-clinic visit with approximately 20 minutes collected at rest. Following the in-clinic data collection, the Holter monitor will be removed, and the subject will be exited from the study.

A summary of the data collected for this study is displayed below in Table 1.

Table 1: AccelAV Data Collection Summary

AccelAV Study Data Collection	Baseline	Micra AV Implant	Echocardiogram	1-month visit	3-month visit
Inclusion/exclusion assessment	X				
Patient informed consent	X				
Demographics and pacing indication	X				
Medical history	X				
Height and weight	X				
12-lead ECG	X				
Blood pressure	X				
Cardiovascular medications	X		X	X	X
Patient symptom checklist	X			X	X
Quality of life questionnaire	X			X	X
Micra AV implant procedure data collection		X			
Accelerometer waveform data collection		X			
Holter monitoring post-implant		X			
X-rays of Micra AV implant location		X			
Echocardiogram			X		
Initial device interrogation			X	X	X
Confirm atrial sensing parameters			X	X	X
In-clinic Holter monitoring				X	X
Ambulatory Holter monitoring				X	
Subject activity log				X	
Final device interrogation		X	X	X	X
Study exit					X
Adverse events	If Occur				
Study deviations					
Device deficiencies					
System modification*					
Unsuccessful implant					
Unscheduled visit					

* If the primary reason for the system modification is pacemaker syndrome then collect the subject's blood pressure and 12-lead ECG prior to the system modification procedure.

6. Determination of Sample Size

A sample size of approximately 150 subjects with usable Holter recordings is required to evaluate the study's objectives. Based on the predicate MARVEL and MARVEL 2 studies it is expected that approximately half, or 75, of these subjects will have a predominant rhythm of persistent 3rd degree AVB and normal sinus node function during the 1-month visit. A sample size of 75 subjects with persistent 3rd degree AVB and normal sinus node function will allow the percentage of AV synchrony during rest to be measured with a precision (distance from point estimate to lower 2-sided 95% CI) of approximately ≤3.5%. Since not all subjects may have usable Holter datasets, up to 175 subjects may be enrolled. See section 7.9.3.4 for a detailed sample size calculation.

7. Statistical Methods

7.1 General Considerations

7.1.1 Analysis Timing

There might be up to two formal statistical analyses. A first formal analysis may happen once all enrolled subjects have completed their 1 month visit and will be related to the primary study objective only. A final formal analysis will then happen once all subjects have had the opportunity to complete their 3 months visit and will be related to the secondary, [REDACTED] objectives of the study. In case the first analysis is not performed, the final analysis will be related to all study objectives. Both analyses will be produced once the study databases have been frozen for analyses.

7.1.2 Type I Error Control

The goal of the AccelAV study is to estimate the rate of AV synchrony in the real-world population rather than test a formal hypothesis with specific type I error control. Therefore, no type I error control is needed.

7.1.3 Usable Holter Datasets

[figure not shown]
A Holter dataset (i.e., device data telemetered to the Holter flash memory and surface ECG recordings) will be considered usable if there is readable telemetry signal as determined by the presence of visible device and algorithm marker channel. Additionally, to be included in the analysis of study objectives that require assessment of AV synchrony (i.e., primary efficacy objective, secondary objective #1, secondary objective #2, [REDACTED]) visible P-waves must be present on the ECG recordings.

7.1.4 Determination of Predominant Heart Rhythm During Holter Monitoring

Holter data from the approximately 30-minute atrial sensing setup during implant and the approximately 5-minute data collection in VDI mode at the 1-month and 3-month follow-up visits will be used to determine each subject's predominant heart rhythm during a Holter monitoring session. The sinus node function will be categorized as normal sinus, sinus node dysfunction (sinus bradycardia, sinus tachycardia, other) or atrial arrhythmia. Subjects without visible P-waves and without evidence of atrial arrhythmias will be classified as having an indeterminate rhythm (e.g. noisy signal, poor electrode placement). The AV conduction status will be categorized as persistent 3rd degree AV block, intact AV conduction, or other (e.g. 2nd degree AVB). Note that subjects with a predominant rhythm of persistent 3rd degree AV block with normal sinus node function will be included in the analysis of the primary efficacy objective.

The AV conduction status will be determined based on the distribution of PR intervals during the 30-minute atrial sensing setup during implant and the approximately 5-minute data collection in VDI mode at the 1-month and 3-month follow-up visits while the Micra AV algorithm is in VDI mode (i.e., no atrial tracking). For each subject, the median PR interval and PR interval interquartile range will be computed. Subjects with intact AV conduction will have a consistent PR interval. Therefore, subjects with an interquartile range of their PR interval <100 ms will be classified as having intact AV conduction (Figure 2, values below dotted line). Subjects with 3rd degree AV block tend to have more uniformly distributed PR intervals. Therefore, for the remaining subjects, i.e., those with a median PR interval exceeding 100 ms, if the median PR interval is within 100 ms of their interquartile PR interval range, they will be classified as having persistent 3rd degree AV block (Figure 2, values between solid lines). For example, a subject with a median PR interval of 300 ms with an interquartile PR interval range lying between 200 and 400 ms would be classified as having persistent 3rd degree AV block. AV conduction status for subjects with a PR interval distribution that falls outside these two criteria or who have a high PVC burden will be determined manually from the ECG Holter recording.

Figure 2: Example of PR Interval Interquartile Range vs Median – Data from MARVEL Study

Notes: Circles indicate MARVEL subjects classified as having intact AV node conduction. Squares indicate MARVEL subjects having persistent 3rd degree AV block.

The sinus node function will be determined based upon the duration of the P-P intervals during both the atrial sensing setup and subsequent VDD mode operation during implant and both the VDD and VDI resting phases at the 1-month and 3-month follow-up visits. P-P intervals greater than the lower rate interval (i.e., 1200 ms at a lower rate of 50 bpm), or P-P intervals less than 600 ms (corresponding to a sinus rate > 100 bpm) will be identified. If these long or short intervals comprise less than 5% of the total P-P intervals during these two procedure steps, then the subject will be classified as having normal sinus node function. If these long or short intervals comprise 5% or more of the P-P intervals, then the ECG will be manually reviewed to classify the subject as having normal sinus node function or sinus node dysfunction. A manual review may also be triggered if the subject has been identified during the study as having an atrial arrhythmia, such as atrial flutter or atrial fibrillation, where the P-waves may not have been identified during the P-wave truthing process.

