7.9.2.3 Accuracy Spreadsheet

A Matlab program will collate 1) the identified P-waves, 2) times corresponding to distinct study procedure steps from the timeline spreadsheet, 3) pacing markers, and 4) Micra AV pacing and supplemental markers into a .csv format spreadsheet, referred to below as an “accuracy spreadsheet.” The accuracy spreadsheet uses the P-wave as the fiducial marker and contains one row of information per truthed P-wave that occurred during the Holter recording. An example of the use of this spreadsheet is to compare the time from a P-wave to the next ventricular event (Column B) to 300 ms to determine if a beat was synchronous. This can be further selected to specific procedure steps (Columns K and L) to characterize the AV synchrony for a specific procedure step, such as the resting period.

Loss of communication between the Holter and the implanted Micra AV, called telemetry dropout, can lead to loss of the pacing markers, supplemental markers, or both. Presence of telemetry dropout and the duration of the dropout is provided in the spreadsheet. In addition, an indication of telemetry in the first 300 ms after a P-wave is provided so that beats with no ventricular sense or pace markers and evidence of telemetry dropout in the first 300 ms after a P-wave can be excluded from analyses. Furthermore, some analyses may rely on valid Micra AV pacing or supplemental markers from the

previous pacing cycle. The times of the preceding markers is provided in the spreadsheet and if these exceed the previous P-P interval, telemetry dropout is implied.

Figure 6 displays an example accuracy spreadsheet. The columns of the accuracy spreadsheet are defined as follows:

1. (A): Time of P-wave in seconds relative to the beginning of the Holter recording
2. (B): Time in seconds from P-wave to next ventricular event (VS or VP)
3. (C): Time in seconds from P-wave to next A4 detection
4. (D): Time in seconds between the ventricular event preceding and following the P-wave (i.e., the R-R interval)
5. (E): Marker code associated with the ventricular event following the P-wave. Codes of 160, 172, or 173 mean a VS and codes of 163 or 164 mean a VP
6. (F): Time in seconds from ventricular event preceding the P-wave to the P-wave
7. (G): Bit encoding for Micra AV algorithm settings at last supplemental marker before the current P-wave. Note Micra AV algorithm settings are decoded in columns (P) and (Q).

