7.9.2.4 Ventricular Event Spreadsheet

Holter datasets will be further analyzed to extract information related to ventricular sensing (including V-V interval). Specifically, a Matlab program will collate each ventricular event, times corresponding to distinct study procedures, and other device markers and information in a .csv file, referred to below as an “VEvent spreadsheet” that will contain one row per ventricular event (i.e., ventricular pace or sense). This contrasts with the accuracy spreadsheet where each row contains information for a P-wave.

Similar to the discussion of the accuracy spreadsheet creation, loss of communication between the Holter and the implanted Micra AV, called telemetry dropout, can lead to loss of the Micra and Micra AV supplemental markers. Note that since this spreadsheet is created from ventricular pacing markers, the loss of a pacing marker can only be inferred from a long interval between ventricular events with evidence of telemetry dropout. Some analyses may rely on Micra AV pacing and supplemental markers from the previous pacing cycle. The times of the preceding markers are provided in the spreadsheet, and if these exceed the previous V-V interval, telemetry dropout is implied.

Figure 7 shows an example VEvent spreadsheet. The VEvent spreadsheet uses the ventricular event as the fiducial marker and contains one record per ventricular event that occurred during the Holter recording. The columns of the VEvent spreadsheet are defined below:

1. (A): Time of ventricular event in seconds relative to the beginning of the Holter recording
2. (B): Marker code associated with the ventricular event. Codes of 160, 172, or 173 mean a VS and codes of 163 or 164 mean a VP
3. (C): Programmed lower rate in bpm
4. (D): Time in seconds from the ventricular supplemental marker prior to the V-Event to the V-Event. The Micra AV algorithm mode and pacing mode are derived from the ventricular supplemental marker. The ventricular supplemental marker is uplinked separately after each V-Event
5. (E): Micra AV algorithm mode at last supplemental marker before the current V-Event (1=VDD/Adaptive, 3=VDI/Monitor)
6. (F): Pacing mode at last supplemental marker before the current V-Event (0=OOO, 1=VOO, 2=VVI, 3=OVO, 4=ODO, 5=VDI, 6=VDD, 10=VVIR, 13=VDIR, 130=VVI40)

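### The automatic rule for persistent 3rd degree AV block in SAP 7.1.4 never checks whether ventricular events are paced, so some 2nd degree and part-conducted recordings can enter the primary cohort unreviewed

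*SAP*

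**What the plan says.** SAP 7.1.4 works in three steps on PR intervals recorded while the device is not tracking the atrium. At the 1-month and 3-month visits this is the roughly 5-minute VDI segment.

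- An interquartile range (IQR) under 100 ms means intact conduction.
- Of the rest, the AV block rule reads: "if the median PR interval is within 100 ms of their interquartile PR interval range, they will be classified as having persistent 3rd degree".
- Manual reading is reserved for stated cases: "subjects with a PR interval distribution that falls outside these two criteria or who have a high PVC burden will be determined manually".

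The third conduction category is given beside the second: "intact AV conduction, or other (e.g. 2nd degree AVB". So 2nd degree block is meant to fall outside the primary cohort.

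The data needed to tell paced from conducted beats already exist. The ventricular event file "will contain one row per ventricular event (i.e., ventricular pace or sense"), and in both spreadsheets "codes of 163 or 164 mean a VP". Section 7.1.4 does not use these codes.

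**The concern.** In complete block without atrial tracking, and with no escape rhythm above the lower rate, ventricular events are paced and unrelated to the P-waves, so PR is spread widely. A wide PR spread can also come from a mixture: conducted beats at a short PR, and blocked P-waves followed by a backup pace. Median and IQR alone cannot always separate the two. The paced share can, because a conducted beat is a sensed event.

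The label decides who enters the primary analysis (7.9.3.5), secondary objective #1 at both visits (7.9.4.4), secondary objective #2, which is built on the primary cohort (7.9.5.4), and, through 7.1.5, the echo cohort of secondary objective #3. It also decides which P-waves are evaluable, since the mode-switch and VVI exclusions in 7.9.3.3 apply only to subjects with this label. A P-wave conducted within 300 ms counts as synchronous without any device tracking. A mislabelled 2:1 subject would therefore tend to raise the estimate.

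**Working it through.** **The rule as coded.** IQR < 100 ms: intact. Otherwise |median − IQR width| ≤ 100 ms: 3rd degree. Otherwise: manual. IQR must be a width, because a median always lies between its own quartiles.

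**The SAP's own example.** Median 300 ms, IQR between 200 and 400 ms. If these are the quartiles, the width is 200 and |300 − 200| = 100, which is inside the band. If they are limits on the width, the band is 300 ± 100. Both readings give the coded rule. Full dissociation, with PR uniform on 0 to 1200 ms, has median 600 and IQR 600: 3rd degree, as intended.

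**Hand example.** The lower-rate interval is the SAP's illustration, "1200 ms at a lower rate of 50 bpm". The rhythm is assumed: 3:2 Wenckebach, P-P 950 ms, conducted PRs 200 and 280 ms, third P-wave blocked.

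- Conducted events at 200 and 950 + 280 = 1230 ms.
- Backup pace at 1230 + 1200 = 2430 ms.
- Blocked P-wave at 1900 ms, so PR = 2430 − 1900 = 530 ms.
- The next P-wave, at 2850 ms, conducts and the cycle repeats.

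PRs are 200, 280 and 530 in equal parts: median 280, IQR 530 − 200 = 330, difference 50. The label is 3rd degree with no review. Two of three P-waves conduct within 300 ms, and one of three ventricular events is paced. A P-P of 950 ms passes the sinus check. Every P-wave has a ventricular event before the next P-wave, so the handling of P-waves without one does not matter here.

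**How far the example reaches.** With lower-rate interval L and P-P p, the blocked PR is p + 280 + L − 2p = L + 280 − p and the IQR is L + 80 − p. The rule requires |p + 200 − L| ≤ 100, so p lies between L − 300 and L − 100. Within P-P 640 to 1000 ms this gives 900–1000 ms at 50 bpm (L = 1200), 700–900 ms at 60 bpm (L = 1000), and nothing at 40 bpm (L = 1500).

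**Simulation.** Assumptions: 5-minute VDI segments, P-P 640–1000 ms with SD 3%, conducted PR 160–280 ms, Wenckebach increments of 80 ms (3:2) or 70 and 110 ms (4:3), conducted beats within 250 ms of a ventricular event lost, all P-waves used. At 60 bpm, 21 of 133 settings are left out because their long P-P intervals would trigger the sinus review. Share labelled 3rd degree without review:

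| Pattern | 40 bpm | 50 bpm | 60 bpm |
|---|---|---|---|
| 2:1 block | 43% | 76% | 62% |
| 3:2 Wenckebach | 0% | 40% | 58% |
| 4:3 Wenckebach | 13% | 7% | 16% |
| Conduction for half the segment | 0% | 29% | 65% |
| Steady 1:1 | 0% | 0% | 0% |

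Counting only P-waves with a ventricular event before the next P-wave changes the figures (2:1 becomes 27/62/60%) but not the conclusion.

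**With a ≥ 90% paced requirement.** The 2:1, 3:2, 4:3 and half-segment patterns fall to about 1% or less (1.8% at most if the 21 settings are kept). At 50 bpm, with slightly wider P-P and PR ranges, conduction of a random 30% of P-waves falls from 73% to 0%. Random 10% conduction falls only from 90% to 30%. In a run across lower rates, about 5/26/61% of the 10% recordings at 40/50/60 bpm kept the label after the check.

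**Size of bias.** The planning synchrony is 89.2% (SAP 7.9.3.4). Assume that a 2:1 subject conducts half of P-waves within 300 ms and that the blocked half is tracked at 89.2%: 0.5 + 0.5 × 0.892 = 0.946, or 5.4 points above 89.2%. The mislabelled share is an assumption: 5% gives 0.05 × 5.4 = 0.3 points, 10% gives 0.5, 20% gives 1.1. The planned median distance to the lower limit at n = 75 is 88.76 − 85.87 = 2.9 points (SAP Table 2).

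**The case against.** The strongest reply is that this matters little. The study only estimates, with no hypothesis test and no performance requirement, so no decision can flip. The endpoint counts sensed events by definition. The label describes a predominant rhythm, so a few conducted beats need not make it wrong. The modelled rhythms hold a fixed ratio for five minutes, and the results swing with the lower rate. All of this stands, and it limits the size of the point. It does not supply a check on the label: the P-P review concerns sinus function, the general Holter review in 7.9.1 covers recording time, quality and feature operation, and the analysis in subjects with more than 40% ventricular pacing (7.9.3.7) takes any conduction status, so it does not screen the primary cohort.

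Four stronger readings are tempting and not supported.

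- The simulated shares might be taken as misclassification rates. They show what the rule permits under assumed rhythms; they are not patient frequencies.
- The seven MARVEL 2 subjects with other rhythms might be taken as a guide to how many would be mislabelled. They are listed apart from the 40, so they were recognised as not 3rd degree, and their rhythms are not given.
- A large downward bias might be inferred from Wenckebach beats conducted later than 300 ms. That needs assumptions about tracking of those beats that the documents do not supply. For that pattern even the sign is open.
- The Figure 2 legend, "Circles indicate MARVEL subjects classified as having intact AV node conduction. Squares indicate MARVEL subjects having persistent 3rd degree AV block", might be read as proof that the band was never set against 2nd degree block. The plot is not visible to us and is presented as an example, so nothing rests on it here.

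**Conclusion.** The point holds as a gap in the specification. Applied as written, SAP 7.1.4 can label as persistent 3rd degree block some rhythms that it elsewhere assigns to other, and nothing later in the plan catches them. Steady 1:1 conduction is removed correctly in the simulation, and many mixed recordings do go to manual review. The hand example rests only on the SAP's rule, its example lower rate and one assumed rhythm. The likely effect on the primary estimate is modest, about +0.5 points per 10% of the cohort in 2:1 block. That figure depends on an assumed share and on blocked P-waves being tracked at the MARVEL 2 rate. The number of affected subjects cannot be derived from the documents. The change is worth making because the label defines the population being described and the check is cheap.

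**What to change.** In SAP 7.1.4, accept the automatic 3rd degree label only if at least about 90% of ventricular events in the VDI segment are paced (VEvent spreadsheet column B, codes 163 and 164, filtered by procedure step). Apply the same condition to the atrial sensing setup segment used through 7.1.5. Send other in-band recordings to the existing manual ECG review, with readers blinded to the synchrony results, and report how many labels change. The 90% is illustrative and should be fixed before the labels are applied. It must trigger review, not exclusion.

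The check will not catch sparse scattered conduction, about 10% of P-waves or less. There 3rd degree block may still be the predominant rhythm.

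The cost is a sentence or two in the SAP, a few lines of code on existing columns, and extra manual reviews by the same reviewers. Those reviews will include true complete block with an escape rhythm above the lower rate, and the documents do not say how many such subjects to expect. Fully paced complete block passes a paced-share check by construction, so the simulation does not measure this cost.

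As editorial tidy-up only: the wording "for the remaining subjects, i.e., those with a median PR interval exceeding 100 ms" does not match the preceding split on the IQR and should refer to an IQR of 100 ms or more. The text should also state that IQR is a width, that PR is accuracy spreadsheet column B, and whether P-waves with no ventricular event before the next P-wave (column M = 0) are included.
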